4.5.11 Patient-Reported and Clinician-Reported Outcomes

PRO data will be collected via questionnaires to document the treatment benefit of pirfenidone. ClinRO data will be collected using a scale for patient clinical assessment at baseline. The validated scales and questionnaires, translated into the local language as required, will be completed in their entirety at specified timepoints during the study.

To ensure instrument validity and that data standards meet health authority requirements, questionnaires will be self-administered before the patient or clinician receives any information on disease status, prior to the performance of non-PRO assessments, and prior to the administration of study treatment, unless otherwise specified.

4.5.11.1 Borg Scale

The Borg Scale is an instrument to be self-administered by the patient as part of the 6MWT procedure (Borg 1982) (see [Appendix 4](#)). The Borg scale should be printed on heavy paper (11 inches high and perhaps laminated) in 20-point type size. At the beginning of the 6-minute exercise, the patient should tick the answer to the question: *“Please rate the current severity of your breathlessness by circling the most appropriate number on the following scale.”* At the end of the exercise, the patient should grade his breathing level again.

Study staff will enter the 6MWT data into the eCRF.

4.5.11.2 EuroQol 5-Dimension Questionnaire

The European Quality of Life (EuroQol) 5-Dimension Questionnaire, 5-level version (EQ-5D-5L), is a self-report health status questionnaire that consists of six questions used to calculate a health utility score for use in health economic analysis (EuroQol Group, 1990; Brooks 1996; Herdman et al. 2011; Janssen et al. 2013; Jindal et al. 2011; Behr J et al. 2013).

There are two components to the EuroQol EQ-5D: a five-item health state profile that assesses mobility, self-care, usual activities, pain/discomfort, and anxiety/depression, as well as a visual analogue scale (VAS) that measures health state. Published weighting systems allow for creation of a single summary score. Overall scores range from 0 to 1, with low scores representing a higher level of dysfunction. The EQ-5D will be utilized in this study for economic modeling.

Pirfenidone—F. Hoffmann-La Roche Ltd

EQ-5D-5L questionnaire (Self-completed version on paper 1.0) will be used in the study. A sample of the validated questionnaire in English (for UK) is provided in [Appendix 5](#). A validated version (Self-completed version on paper 1.0) in a local (Russian) language will be given to the patients for completion. The questionnaire will be administered on the visits as outlined in the schedule of activities (see [Appendix 1](#)) and prior to any interventions. The patients will be provided with a hard copy of a questionnaire and a pen. Patients should be given ample time for questionnaire completion.

4.5.11.3 GAP Risk Assessment System

The GAP (Gender, Age, Physiology) risk assessment system is a validated clinical prediction tool for estimating prognosis in patients with IPF. It consists of two complimentary prognostic tools intended to inform, but not replace clinical judgment.

First, the GAP index and staging system provides a simple screening method for determining the average risk of mortality of patients by GAP stage. Second, the GAP calculator provides an estimation of individual risk of mortality for those patients in whom a more precise estimation of risk may further inform patient care (see [Appendix 6](#)).

The GAP risk assessment system is utilized at baseline only. Points for each variable of the scoring system will be entered by the investigator directly into the eCRF. GAP index and an estimation of individual risk of mortality will be calculated automatically by the system (Ley et al. 2012).

GAP risk assessment is utilized on the basis of predicted DL_{CO} values. The formulas for computing predicted DL_{CO} are as follows (Crapo and Morris 1971):

Predicted DL_{CO} for men $0.410 \times \text{height (cm)} - 0.210 \times \text{age (yr)} - 26.31$

Predicted DL_{CO} for women $0.282 \times \text{height (cm)} - 0.157 \times \text{age (yr)} - 10.89$.

4.5.12 IPF Care Program

IPF Care Program is a program developed by the Sponsor to support patients with the debilitating lung disease, who are enrolled in the study. The program is implemented to improve patients' compliance to the study treatment and reduce number of drop-outs. The program consists of telephone calls to the patient scheduled at specific timepoints and voluntary information materials for patients.

Pirfenidone—F. Hoffmann-La Roche Ltd

Telephone calls

Telephone calls to patients will be scheduled at Weeks 3, 5, 7, 13 and 24. Additional calls can be performed at Weeks 8 and 10 as needed. A total of 5-7 calls are scheduled in the study. Topics for discussion will include the following:

- Explanation of the IPF disease nature
- Pirfenidone titration and dosing
- Management of side effects
- Everyday life
- Answering questions
- Necessity of additional calls.

A detailed schedule of calls and topics for discussion at each timepoint is presented in [Appendix 7](#).

Investigator should record in the eCRF the date and time of the IPF Care Program calls.

Information materials

The following materials will also be provided to all patients participating in the trial:

- Patient information brochure (information on treatment with pirfenidone)
- Pocket guide (brief information on treatment with pirfenidone)

The materials will be supplied by the Sponsor and dispensed by the investigators or other designated staff. Samples of the IPF Care Program will be provided to the study sites as separate documents.

4.5.13 *Details on the Study Visits*

Before starting any study specific procedures, investigator must have HRCT and surgical biopsy (if applicable) performed in routine practice *confirming diagnose of IPF* to assess eligibility of patient..

Pirfenidone—F. Hoffmann-La Roche Ltd

105/Protocol ML39355, Version 2 dated 09-Jun-2018

4.5.13.1 Informed Consent Visit

Written informed consent must be obtained before initiating any study-associated procedures or changes to a pre-existing treatment regimen for purposes of this study. Informed Consent Visit *is* performed for explaining the study, collecting Informed Consent, handing out the Patient Information, collecting and sending HRCT or surgical biopsy (if applicable) and also for starting the washout medication prior 28 days to start of treatment. Any patient *identified* for the study, must discontinue all prohibited medications and stop smoking at least 28 days before *the* start of treatment. This is the Washout Period. If a medication must be tapered, tapering must start early enough that the patient has discontinued the drug 28 days before the start of treatment. Written informed consent must be obtained before withdrawing or tapering the patient off prohibited therapies.

After signing *the* Informed consent, the investigator must review and transfer for central review HRCT scans, surgical lung biopsies (if available), which were performed in routine practice, to assess eligibility. (HRCT must be no older than 24 months. Results of the surgical lung biopsy must be no older than 4 years).

The investigator must explain to the patient that entry into the study is not guaranteed.

4.5.13.2 Screening Period (Day -28 to Day -1)

Procedures conducted during Screening will be used to determine the eligibility of each patient for study enrollment before initiation of treatment and to establish patient baseline status. If patients fail Screening due to a condition that subsequently resolves (e.g., infection), they may be considered for rescreening; however, these patients must be discussed with the study *Medical Monitor* or designee before rescreening. *In case of rescreening, the patient must be reconsented.*

The Screening period is defined as the time between the date of the first Screening procedure and Day -1 and may last up to 28 days. Screening procedures may be conducted on different days within the Screening period, if convenient. The order of procedures is not strict; however, basic requirements to be followed are given in gaps below.

The following procedures will be performed during Screening:

- Demographic data
- Review and update medical history and concomitant medications
- EQ5D questionnaire (should be performed before any other non-PRO assessments)

Pirfenidone—F. Hoffmann-La Roche Ltd

- ECGs (obtained before bronchodilator administration or on a separate day) All ECGs are to be obtained prior to other procedures scheduled at that same time (e.g., vital sign measurements, blood draws) and should not be obtained within 3 hours after any meal.
- Physical examination, vital signs, weight, and height
- Clinical laboratory assessments, including hematology, serum chemistries, serologic tests, and pregnancy test for women of childbearing capacity (blood samples must be drawn in fasted state)
- HRCT scan for baseline assessment (for patients with HRCT scans performed more than 2 months before the treatment period or with scans not meeting the imaging acquisition criteria outlined in Appendix 2)
- Review transbronchial lung biopsy/ BAL;
- Spirometry (FVC) (before and after bronchodilator administration with a 15 min delay). Collection and recording of the retrospective FVC values obtained in clinical practice over the last year.
- 6MWT and Borg Scale
- DL_{CO} (obtained before or 30 min after bronchodilator administration)
- GAP assessment
- Eliciting AEs

4.5.13.3 Start of Treatment (Day 1)

Treatment must be initiated no more than 28 days after the start of screening. All Day 1 procedures must be performed before administration of the study treatment. This study has no Day 0.

The following procedures will be performed on Day 1:

- Directed history (including review of AEs/SAEs, concomitant medications, oxygen use, and hospitalizations)
- EQ5D questionnaire (should be performed before any other non-PRO assessments)
- ECGs. All ECGs are to be obtained prior to other procedures scheduled at that same time (e.g., vital sign measurements, blood draws) and should not be obtained within 3 hours after any meal.
- Physical examination, vital signs, and weight

Pirfenidone—F. Hoffmann-La Roche Ltd

- Clinical laboratory assessments, including hematology, serum chemistries, pregnancy test for women of childbearing capacity (blood samples must be taken in fasted state)
- Spirometry (FVC)
- 6MWT and Borg Scale
- Confirmation of patient eligibility for study participation
- Instruct the patient on how to titrate the dose of study treatment
- Dispense 12-week supply of study treatment. Dosing should start on the Day 1
- Dispense patient diary and instruct patients on how to properly record information using the diary.

4.5.13.4 Week 1 Telephone Assessment (\pm 1 Day)

A telephone interview will be conducted to determine vital status and to assess tolerability of study treatment, patient compliance with dosing, and titration of study treatment.

4.5.13.5 Weeks 2, 4, and 8 (\pm 2 Days)

The following procedures will be performed at Weeks 2, 4, and 8:

- Directed history (including review of AEs/SAEs, concomitant medications, oxygen use, hospitalizations, dosing)
- *ECG (at Weeks 4 and 8 only)/ All ECGs are to be obtained prior to other procedures scheduled at that same time (e.g., vital sign measurements, blood draws) and should not be obtained within 3 hours after any meal.*
- Physical examination, vital signs, and weight
- Clinical laboratory assessments, including hematology, serum chemistries, and pregnancy test for women of childbearing capacity (pregnancy test at Weeks 4 and 8 only)
- Review patient's diary

4.5.13.6 Weeks 12 (\pm 2 Days)

The following procedures will be performed at Week 12:

- Directed history (including review of AEs/SAEs, concomitant medications, oxygen use, hospitalizations, dosing)
- EQ5D questionnaire (should be performed before any other non-PRO assessments)

Pirfenidone—F. Hoffmann-La Roche Ltd

- Physical examination, vital signs, and weight
- Clinical laboratory assessments, including hematology, serum chemistries, and pregnancy test for women of childbearing capacity
- Spirometry (FVC)
- 6MWT and Borg Scale
- Review patient's diary

4.5.13.7 Weeks 16 and 20 (\pm 1 Week)

The following will be performed at Weeks 16 and 20:

- Directed history (including review of AEs/SAEs, concomitant medications, oxygen use, hospitalizations, dosing)
- Physical examination, vital signs, and weight
- Clinical laboratory assessments, including hematology, serum chemistries, pregnancy test for women of childbearing capacity (pregnancy test at Week 20 only)
- Review and dispense new diary, if required.

4.5.13.8 Week 26 (\pm 1 Week)

The following will be performed at Week 26 (on two separate days):

1st day at Week 26:

- Physical examination, vital signs
- Spirometry (FVC)
- 6MWT and Borg Scale

2nd day at Week 26:

- Directed history (including review of AEs/SAEs, concomitant medications, oxygen use, and hospitalizations)
- EQ5D questionnaire (should be performed before any other non-PRO assessments)
- *ECG. All ECGs are to be obtained prior to other procedures scheduled at that same time (e.g., vital sign measurements, blood draws) and should not be obtained within 3 hours after any meal.*
- Physical examination, vital signs, and weight
- Clinical laboratory assessments, including hematology, serum chemistries, pregnancy test for women of childbearing capacity

Pirfenidone—F. Hoffmann-La Roche Ltd

- HRCT
- Spirometry (FVC) 6MWT and Borg Scale
- Collect patient's diary

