⁴ Complete physical examination is performed at the Screening only (head, eyes, ears, nose, and throat, and the cardiovascular, dermatological, musculoskeletal, respiratory, gastrointestinal, genitourinary, and neurological systems). At subsequent visits (or as clinically indicated), only limited, symptom-directed physical examinations should be performed.

⁵ Height is assessed at the Screening only.

⁶ ECG should be performed after patient's resting in a supine position for at least 10 min, prior to other procedures scheduled at that same time (e.g., vital sign measurements, blood draws), bronchodilator administration and within 3 hours after any meal)

⁷ To confirm IPF will be applicable to use previously performed HRCT, if it is performed not earlier than 24 months before the Screening. Review of the SLB samples obtained within 4 years before the Screening should be performed centrally for eligibility confirmation. Histopathological evaluation, if not available, is not repeated at the Screening.

⁸ Transbroncheal biopsy or BAL are not mandatory and will only be reviewed at the Screening, if available, to exclude other causes of PF.

⁹ HRCT should be performed at the Screening only for patients having no validated procedure within 2 months prior initiation of treatment.

¹⁰ At screening, spirometry measurements of FVC should be performed before and after administration of albuterol (or sa butamol) from a metered dose inhaler (4 separate doses of 100 mg). Tests should be repeated after a 15-min delay. During further visits, bronchodilator test is not necessary to perform. Collection and recording of the retrospective FVC values obtained in clinical practice over the last year will be performed only *at the screening visit*.

¹¹ Blood samples must be drawn in fasted state. *Serologic tests: rheumatoid factor, anticyclic citrullinated peptide and antinuclear antibody titer.*

¹² Pregnancy test must be performed before first dosing on Day 1 and must be negative. If the urine test is positive, serum pregnancy test must be performed.

¹³ Questionnaires should be self-administered before the patient or clinician receives any information on disease status, prior to the performance of non-PRO assessments, and prior to the administration of study treatment, with the exception for Borg scale administered in conjunction with the 6MWT.

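### The Week 26 EQ-5D is listed only on the second visit day, after first-day spirometry and walk test, which across the visit conflicts with the protocol's own questionnaire-first rule

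*Protocol*

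**What the plan says.** Protocol 4.5.11 sets the general rule: "questionnaires will be self-administered before the patient or clinician receives any information on disease status, prior to the performance of non-PRO assessments". It gives the validity of the instrument and health-authority data standards as the reason. The sentence ends with a let-out: "prior to the performance of non-PRO assessments, and prior to the administration of study treatment, unless otherwise specified". Appendix 1 footnote 13 repeats the rule, "Questionnaires should be self-administered before the patient or clinician receives any information on disease status, prior to the performance of non-PRO assessments", and exempts only the Borg scale, which belongs to the walk test. Protocol 4.5.11.2 adds that the EQ-5D is given at its scheduled visits "and prior to any interventions".

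Protocol 4.5.13.8 then describes Week 26: "The following will be performed at Week 26 (on two separate days". The list headed "1st day at Week 26" contains examination with vital signs, spirometry, and 6MWT with Borg. The EQ-5D is not in it. The form appears only in the second-day list, with the note "EQ5D questionnaire (should be performed before any other non-PRO assessments".

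Change from baseline to Week 26 in EQ-5D is one of two secondary endpoints (Protocol 2; SAP 3.2.2). SAP 8.2 takes the EQ-5D baseline as the last value before first dose, which is normally Day 1. SAP 7 gives the two Week 26 days separate rows with the same window, study Days 169 to 189.

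**The concern.** A site that follows 4.5.13.8 to the letter collects the EQ-5D after the patient has already been examined, done spirometry and walked the test at the same time point. Spirometry is read locally (Protocol 3.1 and 4.5.7), so the site can have an on-treatment FVC before the form is filled in. That first-day FVC is one of the two values averaged into the primary outcome.

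The questionnaire-first rule exists to keep that information away from the patient's answers. The study is open-label and single-arm, so no control group would offset an influence of test order or of known results. The one split visit is also the visit that defines the EQ-5D endpoint.

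**Working it through.** No sample-size or error-rate figure is involved. The check compares the rule with each visit list.

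**Step 1. Position of the form at each EQ-5D time point**

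| Time point | Protocol section | EQ-5D relative to that time point's spirometry and 6MWT |
|---|---|---|
| Screening | 4.5.13.2 | Before (procedures may be spread over several days) |
| Day 1 | 4.5.13.3 | Before |
| Week 12 | 4.5.13.6 | Before |
| Week 26 | 4.5.13.8 | After the first-day tests, before the second-day tests |
| Week 52 | 4.5.13.10 | Before |

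Only Week 26 puts a testing session of the same time point ahead of the form.

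**Step 2. Does the rule run per day or per visit?** The protocol does not say. The rule has two parts.

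- *Before non-PRO assessments.* Read per day, this is met, because the second-day form is to precede the other second-day assessments. Read per visit, it is not met: one examination, one spirometry and one walk test come first.
- *Before disease-status information reaches patient or clinician.* A per-day reading does not rescue this part. First-day FVC is read at the site, lung-function tests in one patient should be done by the same investigator (4.5.7), and nothing says that first-day results are withheld until the form is complete.

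**Step 3. Is Week 26 one time point?** For the analysis, yes. FVC and 6MWT are each averaged over the two days (Protocol 6.4.1 and 6.4.2; SAP 8.1 and 8.2). The two SAP window rows share the same limits, so they do not define different time points.

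**Step 4. How far apart can the two days be?** No maximum gap is stated. Within the shared SAP window it could reach 189 − 169 = 20 days.

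**Step 5. Comparison with baseline.** The Day 1 form precedes the Day 1 tests, but Screening has already included spirometry, 6MWT and DLco on an earlier day. Treatment must start within 28 days of the start of screening, so those tests lie up to 28 days back. Both ends of the EQ-5D change therefore normally follow an earlier testing day. Two differences remain: the interval may not be the same, and Screening results predate treatment while first-day Week 26 results do not.

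**Step 6. The schedules.** In the text as extracted, the EQ-5D mark in Appendix 1 lines up with the first Week 26 Borg mark. In the synopsis schedule and SAP Table 1 it lines up with the second. This may be an artefact of the PDF, so it needs checking rather than counting as an error.

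**The case against.** The case for leaving the plan alone has four parts.

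- *The rule is met day by day, and 4.5.11 allows exceptions.* This stands in part. The note sits inside the second-day list and is satisfied there. It is not a declared exception, though: 4.5.13.8 restates the rule instead of relaxing it, and footnote 13 exempts only Borg. The disease-status part stays open on either reading. The extra words in 4.5.11.2 add little, since spirometry and walk tests are assessments rather than interventions.
- *Baseline has the same structure.* This largely stands. A reader might infer that the form comes first at baseline and after testing at Week 26, so that the change is systematically biased. The documents do not support so sharp a contrast, because the Day 1 form also follows Screening tests on an earlier day.
- *On-treatment results are known anyway.* This stands. Week 12 spirometry and 6MWT are done on treatment and spirometry is read locally, so reordering Week 26 cannot remove all open-label knowledge. No passage says that first-day results are given to patients.
- *Moving the form creates its own small mismatch.* This is true: the Week 26 form would no longer sit on the second of two testing days, as the Day 1 form does.

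**Conclusion.** The conflict is real at visit level, and on the disease-status requirement a same-day reading does not remove it. It concerns every patient who attends Week 26 as scheduled, at the time point that defines one of two secondary endpoints. The order of procedures is certain from the text. The conflict rests on treating the two Week 26 days as one time point, as the FVC and 6MWT analyses do.

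Two stronger conclusions are tempting and do not follow. One is that the schedule plainly breaks the rule: the protocol never says whether the rule runs per day or per visit. The other is that the reported EQ-5D change carries a bias of some number of points. The documents give neither a size nor a direction for an order effect, and any figure would be invented. What remains is an internal inconsistency on a validity safeguard that the protocol set for itself, and it is cheap to remove.

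**What to change.** In Protocol 4.5.13.8, make the EQ-5D the first procedure on the first Week 26 day, ahead of examination, spirometry and 6MWT, and delete it from the second-day list. This meets the rule whether it is read per day or per visit, and it matches Weeks 12 and 52. Make the synopsis schedule, Appendix 1 and SAP Table 1 show the mark in the same Week 26 column. The cost is one moved line and the matching schedule marks, with no added visit or procedure, plus the small mismatch with the Day 1 form noted above.

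For patients already past Week 26, do not drop forms dated after the first Week 26 spirometry. Sites that followed the protocol will have produced almost only such forms, so an analysis without them would keep mainly deviations. Instead, report the order as a limitation and give the interval between first-day spirometry and the EQ-5D. SAP Listings 18 and 21 already carry the assessment dates, so no new data are needed.
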